This study's primary object is to assess the safety of the study drug. Descriptive efficacy statistics for the endpoints will assist in evaluating compliance with treatment for the purposes of safety assessment.

The efficacy endpoints include the following:

- Complete Cure, defined as 0% clinical involvement of the target toenail and negative KOH and fungal culture at Week 52
- Complete or Almost Complete Cure at Week 52, defined as :: 5% toenail involvement
- Clinical Efficacy rate at Week 52, defined as an affected target great toenail area of <10%
- Mycologic Cure rate at Week 52, defined as a negative KOH examination and a negative fungal culture of the target great toenail sample

The Complete Cure rate, the Complete or Almost Complete Cure rate, the Clinical Efficacy rate, and the Mycologic Cure rate will be presented using descriptive statistics (sample size n, frequency counts and percentages) for the Safety, PK and Non-PK populations. In addition, the growth of the target great toenail at each study visit and the change from baseline in the number of affected nontarget toenails will be descriptively summarized.

A last observation carried forward (LOCF) imputation will be used to impute missing values for the efficacy variables at Week 52. No sensitivity analyses will be conducted.

Any subjects remaining (i.e., have not been treated for 48 weeks) will be followed until completion. The final report will be amended with data on these subjects.

Pharmacokinetics:

All subjects in the PK subset who receive at least 1 confirmed dose of study drug and have any PK data on Days 28 and 29 will be included in the PK analysis set. Blood samples will be tested for plasma concentrations of efinaconazole and metabolites (H3 and H4). No imputations will be made for missing data. Plasma concentrations that are reported as below the limit of quantitation (BLQ) in the data transfer file will

be set to zero for the summaries of concentrations as well as calculation of PK parameters. Missing values will be treated as if they were never drawn. Plasma concentrations of efinaconazole and metabolite (H3 and H4) and PK parameters will be summarized using descriptive statistics (n, mean, SD, standard error of the mean [SEM], coefficient of variation [CV], median, minimum, and maximum). Geometric means will also be used to summarize C_{max} , C_{min} , $AUC_{(0-t)}$ and $AUC_{(0-24h)}$.

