Subjects in the PK subset will not apply study drug the night prior to the Week 4 (Day 28) visit. Following the Day 28 study procedures, subjects in the PK subset will undergo timed blood collections to assess plasma concentrations of efinaconazole and metabolites (H3 and H4). Assessments will require collection of approximately 4 mL of whole blood at each time point (approximately 20 mL total). Within 1 hour after the predose blood sample is drawn, the subjects/parents/legal guardians will apply study drug to all 10 toenails at the investigational center. Subsequent blood collections will occur 2, 4, and 12 hours postdose on Day 28. The subjects will go home after Day 28, but will not apply study drug on the night of the Day 28 visit. All PK subjects in the 4-Week trial will return to the investigational center the following day (Day 29) for collection of a 24-hour postdose blood sample, and exit the study. PK subjects that consented 52-week trial will continue treatment with study drug to only the target great toenail and the other affected toenails and return to the investigational center at Weeks 8, 12, 16, 20, 24, 28, 32, 36, 40, 44, and 48, and a 4-week post-treatment follow-up visit (Week 52).

Safety will be assessed by reviewing the occurrence of AEs and local skin reactions, assessing vital sign measurements and abbreviated physical examination findings, and noting any additions or changes in concomitant medication uses. Blood samples will be collected at Screening, at Week 4 (Day 28) only for PK subjects who have consented to only 4 weeks of treatment, and at Week 48 for routine safety laboratory evaluations (serum chemistry, hematology, and urinalysis); urine pregnancy tests will be obtained for all FOCBP at each study visit. Efficacy assessments will be performed throughout the study. Efficacy analyses will be based on microscopic examination and mycological culture results for the target great toenail, the percent involvement of the target great toenail, the length of the unaffected part of the target great toenail, the growth of the target great toenail, and the number of affected nontarget toenails.

A post-treatment follow-up visit will occur 4 weeks after the last treatment visit for each subject who continues through Week 48 (ie, at Week 52). Subjects who discontinue from the study prior to Week 48 will return to complete the Week 48 study procedures.

The study design and schedule of assessments is presented in [Table 1](#)

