16. If this is the Early Termination Visit, record the reason for subject discontinuation from the study and complete the Week 48 eCRF. If this is not an Early Termination Visit, the subject should be scheduled to return for the Visit 15 (Week 52) study visit.

11.1.7 Visit 15 (Week 52 [\pm 5 days]) Post-Treatment Follow-up Visit / Study Exit

For all subjects who continue through the Week 48 visit, this visit should occur 4 weeks after the last treatment visit.

The following procedures will be conducted at this visit:

1. Record any AEs (query subject and their parent/legal guardian, "Are there any changes in your health since the last visit?").
2. Record local skin reaction scores reported by the subject and parent/legal guardian.
3. Review concomitant medications.
4. Clip the toenails.
5. Measure the target great toenail growth since the Baseline Visit (distance from proximal nail fold to transverse notch).
6. Conduct the investigator's assessment of the target great toenail, with a determination of the percentage of toenail affected with disease. Measure the distance from the proximal nail fold to the proximal onychomycotic border.
7. Perform the investigator's assessment of the nontarget toenails for the presence or absence of onychomycosis.
8. Obtain specimens from the target great toenail for fungal culture and KOH examination and send to the mycology central lab per instructions provided in the laboratory manual.
9. Take close-up photographs of the target great toenail. The first photograph will be taken after toenail clipping. After that photograph is taken, the investigator/evaluator will use a fine tipped marker to outline the area affected on the target great toenail. When the marker ink has dried, a second close-up photograph will be taken.
10. Conduct a urine pregnancy test on FOCBP subjects.
11. Exit the subject from the study.

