12.1.6 Efficacy for Assessing Treatment Compliance

This primary objective of this study is to assess the safety of the study drug. Descriptive efficacy statistics for the endpoints will assist in evaluating compliance with treatment for the purposes of safety assessment. The efficacy variables evaluated in this study include microscopic KOH examination and mycological culture outcomes of the target great toenail, percent involvement of the target great toenail, growth of the target great toenail, and assessments of the nontarget toenails. The efficacy endpoints include the following:

- Complete Cure, defined as 0% clinical involvement of the target toenail and negative KOH and fungal culture at Week 52
- Complete or Almost Complete Cure at Week 52, defined as :: 5% toenail involvement
- The Clinical Efficacy rate at Week 52, defined as an affected target great toenail area of < 10%
- The Mycologic Cure rate at Week 52, defined as a negative KOH examination and a negative fungal culture of the target great toenail sample

The Complete Cure rate, the Complete or Almost Complete Cure rate, the Clinical Efficacy rate, and the Mycologic Cure rate will be presented using descriptive statistics (sample size n, frequency counts, and percentages) for the safety, PK, and non-PK populations. In addition, the growth of the target great toenail at each study visit and the change from baseline in the number of affected nontarget toenails will be summarized descriptively.

A last observation carried forward (LOCF) imputation will be used to impute missing values for the efficacy variables at Week 52 for the non-PK population analyses. No sensitivity analyses will be conducted.

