12.8.1 Analysis Populations

All subjects who receive at least 1 confirmed dose of study drug will be included in the safety population.

All subjects in the PK subset who receive at least 1 confirmed dose of study drug and have any PK data on Days 28 and 29 will be included in the PK population.

All safety population subjects who are not in the PK subset will be included in the Non-PK population.

12.S.2 Sample Size Determination

Approximately 60 subjects will be enrolled and receive treatment with study drug.

Approximately 20 of the 60 subjects will be enrolled in the PK subset. These sample sizes were based on PK and clinical considerations; no formal sample size calculation was performed. The numbers of planned subjects are considered adequate for determining the safety profile and the PK parameters of efinaconazole in a pediatric population of subjects aged 6 to 16 years 11 months with mild to severe onychomycosis of the toenails.

12.S.3 Handling of Missing Data

No imputations will be made for analyses of safety or PK endpoints. The efficacy endpoints at Week 52, which are used to assess treatment compliance will have missing data imputed with the last observation carried forward (LOCF) for non-PK population analyses.

12.S.4 Multicenter Issues

The study will be conducted at multiple investigational centers in the US and the Caribbean with the intention of pooling the results for analysis.

12.S.5 Multiplicity Issues

Not applicable.

12.S.6 Windowing Rules

The timing of all study visits is relative to the Baseline (Day 1) visit. Visit 3 (Week 4) should occur within 5 days of Day 28, (except for the PK-subset; Visit 3 should occur within 1 day of Day 28) and Visit 3A (Week 4) should occur 1 day after Visit 3. The Week 8 and all subsequent visits should occur within 5 days of the targeted times.

13 Quality Control and Quality Assurance

This study will be conducted under the sponsorship of Valeant, in conformation with all appropriate local and federal regulations as well as ICH guidelines.

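### LOCF fills the off-treatment Week 52 cure endpoints with treatment-period or early-termination values, the possible bias has no fixed direction, and the plan rules out the analyses that would show its size

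*Combined protocol and SAP*

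**What the plan says.** All references are to the current version of the protocol, the one that lets PK subjects choose a 4-week or a 52-week course.

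- **Endpoints (Section 12.1.6).** All four are set at Week 52. Complete Cure is "0% clinical involvement of the target toenail and negative KOH and fungal culture at Week 52". The mycologic endpoint is "The Mycologic Cure rate at Week 52, defined as a negative KOH examination and a negative fungal culture of the target great toenail sample". The other two use affected nail area alone (at most 5%, and below 10%).
- **Who has a Week 52 visit.** Section 11.1.7 says: "For all subjects who continue through the Week 48 visit, this visit should occur 4 weeks after the last treatment visit". Section 7.2 has the same limit. Section 11.1.6 books the visit only when Visit 14 is not an early-termination visit. The synopsis has no such limit and gives the follow-up visit to each subject.
- **Imputation.** Section 12.1.6 applies LOCF to "missing values for the efficacy variables at Week 52 for the non-PK population analyses", and Section 12.8.3 agrees: "carried forward (LOCF) for non-PK population analyses". The synopsis names no population: "A last observation carried forward (LOCF) imputation will be used to impute missing values for the efficacy variables at Week 52".
- **Sensitivity.** Section 12.1.6: "No sensitivity analyses will be conducted".
- **Values available to carry.** After baseline, mycology and nail area are assessed at Weeks 12, 24, 36, 48/early termination and 52 (Sections 11.2.5.1 and 11.2.5.2).
- **Early terminators (Section 8.3).** They return for the Week 48 assessments when possible, with no stated interval after the last dose, and may start other therapy.
- **Interim (Section 12.7).** It contains every table and listing of the final analysis, at a date the sponsor chooses.

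**The concern.** The Week 52 definition asks whether the nail is clear and the mycology negative after four weeks without drug. A subject who stops early has no scheduled visit at which that can be observed, so these missing values are built into the visit schedule. LOCF then supplies a result from a different state: on treatment, or at an early-termination visit an unspecified time after the last dose, possibly after another therapy has begun. No rule says whether a value obtained after such therapy may be carried. A subject who completes Week 48 but misses Week 52 also has an end-of-treatment value carried.

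The resulting percentage is labelled a Week 52 rate but mixes two kinds of status, and the plan forbids the comparison that would show how much of it is imputed. The interim adds to this. Subjects still under treatment at the cut have no Week 52 value, and nothing in the text stops LOCF from filling it with an on-treatment result. The share affected could then be much larger than dropout alone.

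**Working it through.** The plan states no dropout rate, cure rate or power calculation, so there is no figure of its own to reproduce. Every rate below except N is an assumption.

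**Inputs.** About 60 subjects, about 20 of them in the PK subset (Section 12.8.2), so N = 60 - 20 = 40 non-PK subjects. Let m be the number missing Week 52, d = m/N, x the number of observed cures, and a the share of missing subjects whose carried value is a cure.

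**1. LOCF minus missing-as-not-cured = d × a.**

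- Low: 0.10 × 0.30 = 3 points.
- Middle: 0.15 × 0.50 = 7.5 points, which is 3 of 40 children.
- High: 0.25 × 0.70 = 17.5 points.

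This difference cannot be negative, because one convention sets every missing value to failure. Its sign therefore says nothing about bias.

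**2. LOCF minus observed-case = (x + a·m)/N - x/(N - m).** Take m = 8 (20% missing) and x = 13 of 32 observed. Missing-as-not-cured is 13/40 = 32.5%; observed-case is 13/32 = 40.6%.

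| a | LOCF | LOCF minus observed-case |
|---|---|---|
| 0 | 13/40 = 32.5% | -8.1 points |
| 0.5 | 17/40 = 42.5% | +1.9 points |
| 1 | 21/40 = 52.5% | +11.9 points |

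One set of observed data gives a LOCF rate on either side of the observed-case rate.

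**3. LOCF error against true Week 52 status = d × [a·r - (1 - a)·g].** Here r is the chance that a carried cure is not a cure at Week 52, and g the chance that a carried failure is a cure at Week 52. With d = 0.20:

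- a = 0.5, r = 0.3, g = 0: 0.20 × 0.15 = +3.0 points.
- a = 0.5, r = 0.1, g = 0.3: 0.20 × (0.05 - 0.15) = -2.0 points.
- a = 0.1, r = 0.2, g = 0.2: 0.20 × (0.02 - 0.18) = -3.2 points.

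LOCF overstates cure only when a·r > (1 - a)·g. A negative culture taken while drug may still be in the nail is a reason to expect r above zero for mycologic cure. A Week 12, 24 or 36 nail that is still growing out is a reason to expect g above zero for the area endpoints. The documents give neither quantity.

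**The case against.** **Efficacy is only supportive.** Section 12.1.6 makes these statistics descriptive and uses them to help judge compliance; Section 12.8 rules out hypothesis testing. For compliance, an on-treatment result is informative, and recoding every dropout as not cured would mix stopping with non-response. This stands. It limits the weight of the point and argues against making missing-as-not-cured the main rule. It does not justify forbidding the comparison.

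**The other tables already give a check.** The same endpoints are reported for the safety, PK and non-PK populations, and the body confines LOCF to the last. Safety cures minus PK cures would then approximate observed non-PK cures. This stands in part. The reader must reconstruct it; a PK-subset subject without PK data falls in neither subgroup; and the synopsis leaves open whether the safety and PK tables are imputed. PK subjects who choose the 4-week course have no Week 52 data by design, so the percentages in those tables do not serve as a check either.

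**The stronger reading.** A reader might infer that LOCF overstates cure and that the bias always favours the drug. The documents do not support that. The drug-in-the-nail mechanism fits mycologic cure; two endpoints use area alone, and Complete Cure also needs 0% involvement. An early stopper with an uncleared nail is carried as a failure. Nor do the documents establish that every carried value is on treatment, since the timing of the early-termination visit is not stated.

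**Conclusion.** The mismatch is real. In the current body text, treatment-period or early-termination values stand in for a status defined four weeks off treatment, early terminators have no visit at which that status could be observed, and no analysis may show the consequence. The reported non-PK rates may be biased in either direction: upward most plausibly for mycologic cure, downward possibly for the nail-area endpoints.

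The 3 to 17.5 points rest on assumed dropout of 10-25% and 30-70% of dropouts carried as cured. They would equal overstatement only if every carried cure had failed at Week 52 and no carried failure had cleared. They show how far the displayed rate could depend on the convention chosen. No test, sample size or primary objective is affected, so this is a cheap improvement to a descriptive table. Section 12.8 refers to a separate analysis plan whose text is not in the material available, so whether it adds anything could not be checked.

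**What to change.** 1. Delete the sentence in Section 12.1.6 that rules out sensitivity analyses, and its counterpart in the synopsis.
2. For the four binary endpoints in the non-PK population, report observed-case and missing-as-not-cured rows alongside LOCF. Give the number of values imputed and the visit each came from.
3. At the interim, do not use LOCF to fill Week 52 for subjects who have not yet reached that visit; show them as not yet assessed.
4. Reconcile the synopsis with Sections 7.2, 11.1.6 and 11.1.7 on who attends Week 52, and with Sections 12.1.6 and 12.8.3 on the population to which LOCF applies.

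The cost is protocol and analysis-plan wording and two extra rows per endpoint in one descriptive table. The displayed rate may look less favourable. No new data are needed for items 1 to 3.

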12.2 Assessment of Pharmacokinetics

The PK objectives will be considered met when approximately 16 evaluable subjects are treated under maximal use conditions through day 28 and PK samples collected at predose and 2, 4, 12 hrs postdose on Day 28 and 24 hrs postdose on Day 29.

No imputations will be made for missing data. Plasma concentrations that are reported as below the limit of quantitation (BLQ) in the data transfer file and will be set to zero for the summaries of concentrations as well as calculation of PK parameters. Missing values will be treated as if they were never drawn. Plasma concentrations and PK parameters will be summarized for the PK analysis set using descriptive statistics (n, mean, SD, standard error of the mean [SEM], coefficient of variation [CV], median, minimum, and maximum). Geometric means will also be used to summarize C_{max} , C_{min} , $AUC_{(0-t)}$ and $AUC_{(0-24h)}$.

Plasma concentrations of efinaconazole and metabolite (H3 and H4) at each scheduled sampling time point will be summarized using descriptive statistics. The individual plasma concentrations will be listed for each subject. Concentrations BLQ will be displayed as BLQ in the listings.

The mean plasma concentration time profiles for efinaconazole and metabolites (H3 and H4) will be presented graphically for Days 28 and 29 in both linear and logarithmic scales. Individual subject plasma concentration time profiles for efinaconazole and metabolites (H3 and H4) will also be created.

Plasma PK parameters for efinaconazole and metabolites (H3 and H4) will be calculated using noncompartmental analysis. The PK parameters will be calculated for each subject using actual sampling times. The maximum plasma concentration (C_{max}) and time to C_{max} (T_{max}) will be taken directly from the data.

The following PK parameters will be calculated from the individual plasma concentrations on Days 28 and 29 when possible:

- C_{max} (observed peak drug [efinaconazole and metabolites] concentration)
- T_{max} (time at which C_{max} occurs)
- C_{min} (observed minimum drug concentration)
- AUC_{0-t} (area under the concentration-time curve from time 0 up to the sampling time corresponding to the last quantifiable concentration)
- AUC_{0-24h} (area under the concentration-time curve from time 0 through 24 hours [corresponding to the dosing interval])

Additional PK parameters may be calculated as appropriate.

12.3 Subject Disposition

Subject disposition will be summarized for each analysis population.

12.4 Demographics and Baseline Characteristics

Subject demographic and baseline characteristics will be summarized using descriptive statistics for each analysis population.

12.5 Protocol Deviations

All protocol deviations will be reported to the sponsor and recorded throughout the study. A tabulation of protocol deviations will be included in the final study report.

12.6 Compliance

Efficacy evaluations are being conducted to assess treatment compliance. Information regarding the evaluations and their analyses are presented in Section [12.1.6](#).

Study drug compliance will be calculated for each subject by taking into account whether a subject took all doses of study drug as instructed. Calculation of study drug compliance will be documented in the analysis plan.

12.7 Interim Analyses

An interim analysis will be performed to summarize available safety data at a predefined date to be determined by the sponsor. It will be performed for all available data on the PK and non-PK portion of the study. This interim analysis will contain all tables and all listings just like the final analysis, using the locked data for the interim analysis.

12.8 Additional Statistical Considerations

All statistical processing will be performed using SAS® version 9.3 or higher unless otherwise stated. No hypothesis testing will be conducted in this study. A statistical analysis plan, describing all statistical analyses, will be provided as a separate document prior to data analysis.

12.8.1 Analysis Populations

All subjects who receive at least 1 confirmed dose of study drug will be included in the safety population.

All subjects in the PK subset who receive at least 1 confirmed dose of study drug and have any PK data on Days 28 and 29 will be included in the PK population.

All safety population subjects who are not in the PK subset will be included in the Non-PK population.

12.S.2 Sample Size Determination

Approximately 60 subjects will be enrolled and receive treatment with study drug.

Approximately 20 of the 60 subjects will be enrolled in the PK subset. These sample sizes were based on PK and clinical considerations; no formal sample size calculation was performed. The numbers of planned subjects are considered adequate for determining the safety profile and the PK parameters of efinaconazole in a pediatric population of subjects aged 6 to 16 years 11 months with mild to severe onychomycosis of the toenails.

12.S.3 Handling of Missing Data

No imputations will be made for analyses of safety or PK endpoints. The efficacy endpoints at Week 52, which are used to assess treatment compliance will have missing data imputed with the last observation carried forward (LOCF) for non-PK population analyses.

12.S.4 Multicenter Issues

The study will be conducted at multiple investigational centers in the US and the Caribbean with the intention of pooling the results for analysis.

12.S.5 Multiplicity Issues

Not applicable.

12.S.6 Windowing Rules

The timing of all study visits is relative to the Baseline (Day 1) visit. Visit 3 (Week 4) should occur within 5 days of Day 28, (except for the PK-subset; Visit 3 should occur within 1 day of Day 28) and Visit 3A (Week 4) should occur 1 day after Visit 3. The Week 8 and all subsequent visits should occur within 5 days of the targeted times.

13 Quality Control and Quality Assurance

This study will be conducted under the sponsorship of Valeant, in conformation with all appropriate local and federal regulations as well as ICH guidelines.

The sponsor is responsible for implementing and maintaining quality assurance and quality control systems to ensure that studies are conducted and data are generated, documented, and reported in compliance with the protocol, GCP guidelines, and applicable regulatory requirements. In addition, the sponsor will be responsible for securing agreement from all involved parties to ensure direct access to all study-related sites, source data/documents, eCRFs, and reports for the purpose of monitoring and auditing by the sponsor, and inspection by domestic and foreign regulatory authorities.

Central laboratory services will be performed by a qualified, licensed facility that will be listed on the US Food and Drug Administration Form 1572. Copies of all normal values

(as applicable), laboratory certifications, and the director's curriculum vitae will be provided to each investigational center and to the sponsor.

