application technique for the study drug and provide the appropriate Subject Instruction Sheet with dosing instructions (ie, for non-PK or PK subjects), depending on whether the subject is enrolled in the PK subset. Record any AEs following the initial treatment application.

20. Record local skin reactions. Instruct the subject and their parent/legal guardian to report local skin reactions (if any) at each study visit.
21. Schedule the next study visit (Visit 3 [Week 4, Day 28]) in 28 days (\pm 5 days).

Note: (\pm 5 days) only applies to Non-PK subjects, PK subset only has a (\pm J day) visit window

- For subjects in the PK subset, Visit 3 (Week 4, Day 28) to Visit 3A (Week 4, Day 29) remind subjects not to apply study drug the night prior to their Visit 3 (Week 4, Day 28) visit.

11.1.3 Visit 3 (Week 4, Day 28 [\pm 5 days]), Visit 4 (Week 5 [\pm 5 days]), Visit 6 (Week 16 [\pm 5 days]), Visit 7 (Week 20 [\pm 5 days]), Visit 9 (Week 28 [\pm 5 days]), Visit 10 (Week 32 [\pm 5 days]), Visit 12 (Week 40 [\pm 5 days]), Visit 13 (Week 44 [\pm 5 days])

Visits are to be scheduled in reference to Visit 2 (Baseline).

The following procedures will be conducted at this visit:

1. Record any AEs (query subjects and their parents/legal guardians, "Are there any changes in your health since the last visit?").
2. Record local skin reaction scores reported by the subject and parent/legal guardian.
3. Review concomitant medications.
4. Clip the toenails.
5. Measure the target great toenail growth since the Baseline Visit (distance from proximal nail fold to transverse notch). If the most recently applied notch has grown out or has been clipped off, inscribe a new notch adjacent to the proximal nailfold.
6. Collect the diary and study drug bottle from the subject and/or their parent/legal guardian. Weigh the used bottle of the study drug. Record the number of missed doses from the subject diary and review compliance with the subject.
7. Conduct a urine pregnancy test on FOCBP subjects (discontinue any subject from the study who has a positive test result)
8. Obtain 1 bottle of study drug and weigh the bottle, complete the label and drug log, and dispense the bottle to the subject and their parent/legal guardian. Review the dosing instructions with the subject. (Subjects in the PK subset will not be dispensed study drug this day).
9. Dispense diary. (Subjects in the PK subset will not be dispensed a diary this day.)
10. Schedule the next study visit.

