11.2.6 Evaluation of Pharmacokinetics

The PK assessments will be performed on a subset of the study population who will receive treatment under maximal use conditions for 28 days. Plasma samples for determination of efinaconazole and metabolite levels will be collected at the following time points:

- Visit 3 (Day 28): Predose (after all Day 28 procedures are completed). Study drug must be applied within 1 hour after the predose sample is collected. Samples are then collected at 2 (\pm 5 min), and at 4 (\pm 5 min), and at 12 (\pm 15 min) hours postdose.
- Visit 3A (Day 29): 24 (\pm 30 min) hours after Day 28 study drug application.

Materials for sample collection will be provided to the investigational centers by the sponsor or central laboratory. Instructions for processing and shipping samples to the bioanalytical laboratory are contained in the study laboratory manual.

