12.1 Assessment of Safety

12.1.1 Adverse Events

All AEs that occur during the study will be recorded and classified using the Medical Dictionary for Regulatory Activities (MedDRA). Treatment-emergent adverse events (TEAEs) are those AEs that occur or worsen on or after the date of first study drug application. All TEAEs will be summarized by the number of subjects reporting each TEAE, the associated system organ class and preferred term, the severity, and the relationship to study drug for the safety, PK, and non-PK populations. Each subject will be counted only once within a system organ class or a preferred term using the event with the greatest severity or causality, respectively, within each category.

All SAEs will be summarized by the number of subjects reporting each SAE, the associated system organ class and preferred term, the severity, and the relationship to study drug for the safety, PK, and non-PK populations.

All information pertaining to AEs noted during the study will be listed by subject and will include the verbatim term given by the investigator, the associated system organ class and preferred term, the start and stop (if stopped) dates, the seriousness, and the severity of the event. Additionally, any action taken with the study drug, any corrective treatment administered, the outcome, and the relationship to study drug as well as a list of subjects who prematurely discontinue from the study due to an AE will be provided.

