12.1.2 Local Skin Reactions

Local skin reaction scores (redness, swelling, burning, itching, and vesiculation) at each visit will be summarized using frequency tables for the safety, PK, and non-PK populations. Additionally, redness and swelling severity scores will be summarized using descriptive statistics (mean, standard deviation [SD], median, and minimum, and maximum). Subjects with a severity score worse than baseline will also be summarized at each post-baseline visit. The worst score and the last score during the post-baseline period will also be summarized.

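### A dosed PK-subset subject with no Day 28/29 PK data is in neither the PK nor the Non-PK population, so the printed PK column of the safety, disposition and demographic tables depends on reaching PK sampling (minor, wording fix)

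*Combined protocol and SAP*

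**What the plan says.** Section 12.8.1 of the current protocol (the version with the 4-week and 52-week options) defines three populations.

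- Safety: every subject with at least one confirmed dose.
- PK: PK-subset subjects "who receive at least 1 confirmed dose of study drug and have any PK data on Days 28 and 29".
- Non-PK: "All safety population subjects who are not in the PK subset will be included in the Non-PK population".

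PK-subset membership is settled by Baseline. Section 11.1.2 has the site hand out the dosing sheet "depending on whether the subject is enrolled in the PK subset". PK blood comes later. Section 11.2.6 says "Plasma samples for determination of efinaconazole and metabolite levels will be collected at the following time points", and the first of those is the Day 28 predose sample; the last is 24 hours after the Day 28 application.

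The population labels are used well beyond the concentration tables. Section 12.1.1 tabulates treatment-emergent and serious adverse events by severity and "the relationship to study drug for the safety, PK, and non-PK populations". Under section 12.1.2, skin-reaction scores "at each visit will be summarized using frequency tables for the safety, PK, and non-PK populations". Section 12.3 states: "Subject disposition will be summarized for each analysis population". Section 12.4 states: "Subject demographic and baseline characteristics will be summarized using descriptive statistics for each analysis population". Laboratory and vital-sign summaries (12.1.3, 12.1.4) carry the same three labels. Section 12.7 says the interim analysis will contain the same tables and listings as the final one.

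**The concern.** Requiring PK data is natural for concentration and parameter summaries. Here the same requirement also sets the denominator for safety, disposition and demographic tables. It depends on something observed about four weeks after treatment starts, so it selects on what happened under treatment.

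The subjects affected are those who begin on all 10 toenails. Someone who stops in that period, for any reason, disappears from the column labelled PK. Section 8.3 lists severe adverse reactions among the possible reasons for withdrawal, so missing the Day 28 sample can be related to safety. The PK-column rate is too low if those who left had more events than those who stayed, and too high if they had fewer. PK-column disposition cannot record a discontinuation before sampling.

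**Working it through.** **Step 1: set membership.** Take a subject in the PK subset, dosed at Baseline, with no PK sample.

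- Safety: yes (dosed).
- PK: no (no PK data).
- Non-PK: no (in the PK subset).

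No rule in the supplied text places this subject in either split population. The two superseded protocol versions in the file carry the same three definitions. The wording also leaves open whether data are needed on either day or on both; if on both, the condition extends to the Day 29 sample.

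**Step 2: planned counts.** Section 12.8.2 plans about 60 subjects, about 20 of them in the PK subset, which leaves 60 - 20 = 40 Non-PK. With k dosed PK-subset subjects unsampled, the PK column has 20 - k subjects, and PK + Non-PK = 60 - k against Safety = 60.

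**Step 3: shift in a PK-column rate.** Let n = 20, let s be the number of subjects with an event among the n - k sampled, and let a be the number among the k unsampled.

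shift = s/(n - k) - (s + a)/n = (k/n) × [s/(n - k) - a/k]

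The bracket is a difference between two proportions, so the absolute shift is at most k/n = k/20.

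The protocol gives no rate of loss before Day 28. The values of k below are assumptions, chosen only to show the scale. The last column fixes s = 2 and lets a run from 0 to k.

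| k (assumed) | PK column n | PK + Non-PK | Bound on shift | Shift with s = 2 |
|---|---|---|---|---|
| 0 | 20 | 60 | 0 points | 0 |
| 1 | 19 | 59 | 5 points | +0.5 to -4.5 |
| 2 | 18 | 58 | 10 points | +1.1 to -8.9 |
| 3 | 17 | 57 | 15 points | +1.8 to -13.2 |
| 4 | 16 | 56 | 20 points | +2.5 to -17.5 |

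For k = 2 and s = 2 the column prints 2/18 = 11.1% (exact 95% CI 1.4 to 34.7). The figure for all dosed PK-subset subjects is 2/20 = 10%, 3/20 = 15% or 4/20 = 20% (5.7 to 43.7) when 0, 1 or 2 of the unsampled had an event. The bound itself is reached only when every unsampled subject and no sampled subject has the event, or the reverse.

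**Step 4: what can be recovered.** Non-PK is defined by subset membership, so Safety minus Non-PK is exactly the set of dosed PK-subset subjects, sampled or not: 60 - 40 = 20. Event counts and discontinuations follow by the same subtraction. Means do not come from simple subtraction, and medians, minima and maxima cannot in general be rebuilt.

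**The case against.** The strongest reply is that little is lost. The Safety column, the adverse-event listings and the list of discontinuations due to adverse events are complete. Subject counts for the whole dosed PK subset come from two printed columns (step 4). No objective or test rests on the PK safety column: the safety objective covers all subjects aged 6 to 16, section 12.8 rules out hypothesis testing, and no PK versus Non-PK comparison is planned. All of this stands, and it keeps the point minor. What it leaves is a printed column whose label suggests the PK subset but whose content is the sampled part of it, and nothing in the plan tells the reader to subtract.

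A reader might infer that about four subjects will be lost, from the difference between about 20 enrolled and about 16 evaluable. The documents do not support that. Section 12.2 ties the 16 to maximal-use treatment through Day 28 and to samples at all five times, whereas the PK population needs only some PK data. A subject can fail the first condition and still be in the PK column, so 20 - 16 does not estimate k.

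Section 12.8 defers the analyses to a separate SAP. The summary of changes cites agreement with SAP wording, so such text existed. It was not supplied and may define the column differently.

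**Conclusion.** The gap in the definitions is real. As section 12.8.1 is written, the printed PK column of the adverse-event, serious-adverse-event, skin-reaction, disposition and demographic tables is conditional on reaching PK sampling. Laboratory and vital-sign tables are less exposed, since vital signs are summarised only from Week 12 and laboratory change at Week 48.

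The size is unknown. It is zero if every dosed PK-subset subject is sampled, and otherwise at most k/20 in either direction.

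A reader might go further and infer that safety information on the PK subset is lost, or that the study's safety conclusion is biased. Neither follows: pooled results and listings are complete, and counts for the dosed subset can be recovered.

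The same gap would apply at the interim to any PK-subset subject dosed but not yet sampled at that lock. The date is still to be set by the sponsor, so whether there will be any such subject cannot be said.

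The conclusion rests on the protocol text alone and would change if the SAP already defines a PK-subset safety set. Even then, 12.8.1 should be made to agree with it.

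**What to change.** For all safety, disposition and demographic tables, final and interim, define the PK column as all PK-subset subjects who received at least 1 confirmed dose. The two printed columns then sum to Safety (20 + 40 = 60 as planned). Keep the population that requires PK data only for the concentration and PK-parameter summaries, and state whether data on either day or on both are needed.

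Carry the wording through 12.8.1, 12.1.1 to 12.1.4, 12.3, 12.4, the synopsis and the SAP. Section 12.1.6 uses the same labels for the efficacy summaries and should say which PK column it means.

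The cost is one more population label and a footnote wherever the safety n and the PK n differ (for example 20 against 18). No new data or visits are needed. The change removes the selection but does not turn the column into an event rate for treatment of all 10 toenails. The column still pools 4-week and 52-week participants, and the latter treat only affected nails after Day 28 (section 7.2).
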